3.4. Exploratory Clinical Objectives

- Comparing the proportion of participants who become desensitized vs all others (i.e. treatment failures) at week 52 DBPCFC.
- Comparing the proportion of participants who reach SU vs desensitized but SU failures at week 58 DBPCFC.
- Comparing changes in the transcriptomes and phenotypes of tetramer+ T cells from baseline to 52 weeks, 58 weeks, and to 64 weeks.

3.5. Safety Endpoints

- The proportion of participants with only mild AEs (i.e. Grade 1) during the course of the study.
- The proportion of participants with respiratory or abdominal severe AEs (i.e. Grade 3) during the course of the study.
- The proportion of participants who successfully pass a DBPCFC with no or mild objective reactions to a cumulative 2043 mg of the FA allergen at the end of OIT (desensitization, week 52).
- The proportion of participants who successfully pass a DBPCFC with no or mild objective reactions to a cumulative 2043 mg of the FA allergen after 6 weeks off OIT (sustained unresponsiveness, week 58) and subsequent optional DBPCFC at week 64 (please see Appendix 2).

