observation. If the dose is tolerated, the subject will continue on that daily home dose for the normal time interval per protocol. If the subject does not tolerate this dose, the subject should receive the last tolerated dose or a 1-2 step dose reduction the next day (day 3) in the SNP-CRU or at home if the planned dose was previously tolerated. If this dose is tolerated, it will be continued as the daily home dose for the normal time interval, then escalation attempted in the SNP-CRU as noted below. If this dose is not tolerated, then the next dose will be a 1-2-step reduction in dosing, and the dose will be given at the SNP-CRU on the next day (day 4). If this next dose is not tolerated, then a discussion with the PI will ensue to make a decision about whether to continue the subject on active treatment in the study.

If *severe* symptoms (Grade 3, Appendix 3) occur the action should be to treat the subject, and at the study physician's discretion either 1) have them return to the SNP-CRU the next day (day 2) for dosing with a 2-step reduction in dose under observation or 2) discontinue them from the active treatment. If the subject tolerates the dose reduction, then they will remain on that dose for 2 weeks and then return to the SNP-CRU for the dose escalation. A discussion with the PI may ensue to make a decision about whether to continue the subject on active treatment in the study.

If a subject fails dose escalation after three consecutive (with 2-4 weeks between) attempts, he/she will be considered a maintenance failure and the last tolerated dose will be accepted as the maintenance dose.

For a completed dose escalation with no symptoms, participants should be observed for 30 minutes. For mild symptoms, participants should have a one to two-hour post-protocol observation period. For moderate to severe symptoms, the observation period should be at least four hours and up to 24 hours based on symptoms and treatment regimen needed to stabilize the participant. Any subject deemed to have severe allergic reactions to OIT, including hypoxia, hypotension or change in mental status and receives aggressive therapy (e.g., IV fluid resuscitation, mechanical ventilation, more than 2 doses of epinephrine for a life-threatening reaction) at any time should be discussed with the PI and discontinued from active therapy.

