12.3 Grading and Attribution of Adverse Events

12.3.1 Grading Criteria

The study site will grade the severity of non-allergic adverse events experienced by the study subjects according to the criteria set forth in the National Cancer Institute’s Common Terminology Criteria for Adverse Events (CTCAE) version 5.0. This document (referred to herein as the NCI-CTCAE manual) provides a common language to describe levels of severity, to analyze and interpret data, and to articulate the clinical significance of all adverse events. The NCI-CTCAE has been reviewed by the Principal Investigator and has been deemed appropriate for the subject population to be studied in this protocol.

Adverse events will be graded on a scale from 1 to 5 according to the following standards in the NCI-CTCAE manual:

- Grade 1 = mild adverse event.
- Grade 2 = moderate adverse event.
- Grade 3 = severe and undesirable adverse event.
- Grade 4 = life-threatening or disabling adverse event.
- Grade 5 = death.

Events grade 1 or higher will be recorded on the appropriate AE paper case report form (CRF) for this study.

For grading an abnormal value or result of a clinical or laboratory evaluation (including, but not limited to, a radiograph, an ultrasound, an electrocardiogram etc.), a treatment-emergent adverse event is defined as an increase in grade from baseline or from the last post-baseline value that doesn’t meet grading criteria. Changes in grade from screening to baseline will also be recorded as adverse events but are not treatment-emergent. If a specific event or result from a given clinical or laboratory evaluation is not included in the NCI-CTCAE manual, then an abnormal result would be considered an adverse event if changes in therapy or monitoring are implemented as a consequence of the event/result.

Clinical criteria for diagnosing anaphylaxis will be as follows (Sampson, HA, et. Al, 2006⁷⁹):

Anaphylaxis is highly likely when any one of the following 3 criteria are fulfilled:

1. Acute onset of an illness (minutes to several hours) with involvement of the skin, mucosal tissue, or both (eg, generalized hives, pruritus or flushing, swollen lips-tongue-uvula)
AND AT LEAST ONE OF THE FOLLOWING:
 - a. Respiratory compromise (eg, dyspnea, wheeze-bronchospasm, stridor, reduced Peak expiratory flow (PEF), hypoxemia)
 - b. Reduced blood pressure (BP) or associated symptoms of end-organ dysfunction (eg, hypotonia [collapse], syncope, incontinence)

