
Reaction involving one of the following organ systems in which the symptoms are mild:
 
Cutaneous Generalized pruritus, generalized urticaria, flushing, angioedema
 
Upper respiratory Rhinitis, cough unrelated to laryngeal edema or bronchospasm
 
Conjunctival Injection/redness, itching, tearing
 
GI Nausea, abdominal pain (no change in activity level), single episode of vomiting and/or single episode of diarrhea
	
Reaction involving two or more of the following organ systems in which the symptoms are mild:
 
Cutaneous Generalized pruritus, generalized urticaria, flushing, angioedema
 
Upper respiratory Rhinitis, cough unrelated to laryngeal edema or bronchospasm
 
Conjunctival Injection/redness, itching, tearing
 
GI Nausea, abdominal pain (no change in activity level), single episode of vomiting, and/or single episode of diarrhea
	
Reaction involving:
 
Lower respiratory Throat tightness without hoarseness, wheezing, chest tightness, dyspnea, cough that responds to short- acting bronchodilator treatment (including IM epinephrine)
 
AND/OR
 
GI Severe abdominal pain, more than two episodes of vomiting and/or diarrhea
	
Reaction involving ANY of the following with or without other symptoms listed in Grades 1 to 3:
 
Laryngeal edema
 
AND/OR
 
Severe lower respiratory (throat tightness with hoarseness, wheezing, chest tightness, dyspnea, cough) including:
 
a) Refractoriness² to short-acting bronchodilator treatment (including IM epinephrine)
 
AND/OR
 
b) Hypoxia (O₂ saturation ≤92%)
	
Death

---	--	--	--	--------------

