	
OR
 
Reaction involving one of the following organ systems in which the symptoms are moderate:
 
Cutaneous Generalized pruritus, generalized urticarial, flushing, angioedema
 
Upper respiratory Rhinitis, cough unrelated to laryngeal edema or bronchospasm
 
Conjunctival Injection/redness, itching, tearing
 
GI Nausea, abdominal pain (with change in activity level), two episodes of vomiting and/or diarrhea
		
AND/OR
 
c) Respiratory compromise requiring mechanical support
 
AND/OR
 
Cardiovascular Reduced BP with associated symptoms of end-organ dysfunction (e.g., hypotonia [collapse], syncope) defined as:
 
 • Children: low systolic BP (age specific¹) or >30% decrease in systolic BP • Adults: systolic BP of less than 90 mmHg or >30% decrease from baseline 	
--	---	--	---	--

1. Low systolic BP for children is defined as: less than 70 mmHg from 1 month to 1 year of age, less than (70 mmHg + [2 x age]) from 1 to 10 years of age, and less than 90 mmHg from 11 to 17 years of age.

2- For instance, this would include continuous nebulizer or epinephrine iv infusion or more than 3 epinephrine intramuscular injections

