- Comparing the proportion of participants who reach SU vs desensitized but SU failures at week 64 DBPCFC.

Safety Endpoints

- The proportion of participants with only mild AEs during the course of the study.
- The proportion of participants with respiratory or abdominal severe AEs during the course of the study.
- The proportion of participants who successfully pass a DBPCFC with no or mild objective reactions to a cumulative 2043 mg of the FA allergen at the end of OIT (week 52).
- The proportion of participants who successfully pass a DBPCFC with no or mild objective reactions to a cumulative 2043 mg of the FA allergen after 6 weeks off OIT (week 58).

Measurement: A DBPCFC is considered a “pass” if the subject has no dose limiting symptoms (appendix 3) during the challenge (from administration of first dose through observation period lasting 2 hours after administration of the final dose).

- Frequency of anaphylaxis.
- Frequency of use of epinephrine as a rescue medication.
- Frequency of AEs leading to premature withdrawal.
- Frequency of AEs in each treatment regimen leading to discontinuation of extended interval dosing.

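### Section 3.5 ties the severe respiratory or abdominal AE endpoint to Grade 3 alone; on the five-grade scales of 12.3.1 this leaves out a participant whose only qualifying event is Grade 4 or 5

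*Combined protocol and SAP*

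**What the plan says.** Section 3.5 lists two safety proportions based on AE grade. The first is "The proportion of participants with only mild AEs (i.e. Grade 1) during the course of the study". The second is "The proportion of participants with respiratory or abdominal severe AEs (i.e. Grade 3) during the course of the study". In both, the parenthesis names a single grade.

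The synopsis, section 2.4 and the safety endpoints under section 13.2.2 repeat the second endpoint without a grade. Section 13.2.2, for example, has "The proportion of participants with respiratory or abdominal severe AEs during the course of the study".

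Section 12.3.1 sets the grading. Non-allergic events use CTCAE v5.0, with "Grade 3 = severe and undesirable adverse event", then "Grade 4 = life-threatening or disabling adverse event", then Grade 5 for death. Allergic reactions other than anaphylaxis use CoFAR Table 4, which also has five grades. Its Grade 4 column opens with "Reaction involving ANY of the following with or without other symptoms listed in Grades 1 to 3" and includes "Respiratory compromise requiring mechanical support". Anaphylaxis has its own three-stage severity table in the same section.

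Elsewhere, Grade 3 is used for the top level of the three-level list in Appendix 3. For severe reactions, section 6.4.2 writes "symptoms (Grade 3, Appendix 3) occur the action should be to treat the subject", and section 12.2.1 uses the same label for reactions to home dosing.

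**The concern.** A severity endpoint should include everything at or above its threshold. An analyst who programs section 3.5 as written selects events with grade equal to 3. A participant with one respiratory reaction, graded 4, then counts as having had no severe respiratory event. That participant is not in the only-mild proportion either, so across the two proportions they look the same as someone whose worst event was Grade 2. If a reaction that would have been Grade 3 turns out to be Grade 4, the reported severe proportion goes down. In a single-arm study with at most a few such events, one participant is a visible part of the estimate.

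**Working it through.** The plan gives no figure to reproduce. The check is a comparison of texts, followed by arithmetic for scale.

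**1. Is a threshold implied anywhere?** Section 3.5 uses i.e., which defines rather than illustrates, and the companion endpoint uses it the same way for Grade 1. No section says Grade 3 or higher. The stopping rules in the synopsis list CoFAR Grade 4 events separately from severe events other than anaphylaxis, so the protocol does not clearly treat Grade 4 as part of severe.

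**2. Where do the relevant reactions fall?**

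| Reaction | CoFAR Table 4 | Appendix 3 | Anaphylaxis stage (12.3.1) |
|---|---|---|---|
| Wheeze or dyspnea that responds to a bronchodilator | Grade 3 | severe if wheeze with dyspnea | 1 or 2 |
| Laryngeal edema | Grade 4 | severe | not listed by name; stridor and hoarseness are stage 2 |
| Hypoxia (saturation 92% or less) | Grade 4 | not listed | 3 |
| Mechanical respiratory support | Grade 4 | not listed | not listed |
| Severe abdominal pain alone | Grade 3 | severe | not listed; crampy pain is stage 2 |

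On Table 4, the second to fourth rows fall outside a Grade 3 count. The last row stays inside it, because Grade 4 has no gastrointestinal criterion of its own. Abdominal events are lost on Table 4 only when they accompany a Grade 4 feature: severe abdominal pain with laryngeal edema is one Grade 4 reaction. For non-allergic events, CTCAE Grade 4 can apply to either organ system.

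**3. Who is lost?** Only participants with no separate qualifying Grade 3 event. Section 11.2 allows a participant to be terminated from the study after a CoFAR Grade 4 reaction to the product, which leaves less time for such an event to occur.

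**4. Size.** Inputs: N = 72 (section 3.1), assumed all dosed, so that the Safety Sample of section 13.4.1 is also 72.

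- One omitted participant: 1/72 = 1.4 percentage points. Section 5.2 expects severe symptoms during dosing in fewer than 1% of subjects, that is, fewer than 0.01 × 72 = 0.72 participants.
- The synopsis rule acts at more than 3 CoFAR Grade 4 cases, so 3 cases do not trigger it. Suppose all 3 are respiratory, occur in different participants with no separate Grade 3 event, and enter the AE count. (The rule also covers food-challenge reactions, which section 12.2.1 reports separately.) If there are no other qualifying events:
  - Grade 3 only: 0/72 = 0%, exact (Clopper-Pearson) 95% CI 0 to 5.0%.
  - Grade 3 or higher: 3/72 = 4.2%, exact 95% CI 0.9 to 11.7%.

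**5. How likely is any omission?** The food-challenge text in section 5.2 anticipates life-threatening anaphylaxis at under 0.1%. Applying 0.1% per participant is my assumption. The expected number is then 72 × 0.001 = 0.07, and P(at least one) = 1 − (1 − 0.001)^72 = 7.0%. Over an assumed range of 0.05% to 1% per participant, this probability runs from 3.5% to 51.5%.

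**The case against.** The other side has four good points.

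*The grade appears once.* A reader might infer that the endpoint is fixed at Grade 3 throughout the protocol. It is not. Three other statements give no grade, including the one in the statistical section, and an analyst working from section 13.2.2 alone is not limited to Grade 3. This stands, but section 3.5 is then the only place to look for a definition, and the one it gives is too narrow.

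*No scale is named.* If Grade 3 meant the top level of Appendix 3, laryngeal edema would be counted. If it meant stage 3 of the anaphylaxis table, hypoxia would be. This also stands, so the omission depends on the five-grade reading. That reading is the more natural one, because 12.3.1 is the AE grading section and its labels for Grades 1 and 3 match those in section 3.5. The alternatives do not rescue the endpoint either: they make the same reaction count or not count depending on the reader.

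*Nothing is hidden.* A reader might infer that life-threatening and fatal reactions drop out of the safety reporting. The documents do not support that. Events of Grade 1 or higher go on the case report form (12.3.1), SAEs are reported within 24 hours (12.5.1), and the DSMB receives a listing of all reported AEs and SAEs (12.8.2.1). The synopsis has stopping rules for dosing-related deaths and for Grade 4 cases. Section 13.2.2 adds the frequency of anaphylaxis and of epinephrine use. None of these, however, is the proportion of participants with severe respiratory or abdominal events.

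*Such events should be rare, and the endpoint is descriptive.* Both are true. The primary endpoint is the change in CD28, and sample size, alpha and power are untouched.

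**Conclusion.** Wrong as written, with low to moderate severity. On CTCAE and CoFAR Table 4, the section 3.5 definition leaves out a participant whose only qualifying event is Grade 4 or 5. The loss is 1.4 percentage points per omitted participant of 72, confined to one descriptive safety proportion. For allergic reactions it is mainly a respiratory gap, and it would overstate the point to say that the abdominal half is equally affected.

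The conclusion rests on reading Grade 3 on the scales of 12.3.1. The sizes also assume that all 72 participants are dosed. The three-case example and the event rates are illustrations, not predictions.

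**What to change.** In section 3.5, replace the parenthesis with *Grade 3 or higher* and name the scale: CoFAR Table 4 for allergic reactions and CTCAE v5.0 for non-allergic events, as in 12.3.1. Because 12.3.1 stages anaphylaxis on a separate three-level table, add a sentence saying how anaphylaxis enters this endpoint, for instance by also assigning it a Table 4 grade for the analysis. Changing the threshold without naming the scale would leave the ambiguity in place. Use identical wording in the synopsis, 2.4, 3.5 and 13.2.2.

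The cost is a few words in four places, agreed before the safety analysis. Events of Grade 1 or higher are already recorded, so no new data collection is expected, apart from any Table 4 grade added for anaphylaxis. Sample size, alpha and power do not change.

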3.6. Stratification, Randomization, and Blinding/Masking

There will be no stratification, randomization or blinding in the arms of the study.

4. Selection of Participants and Clinical Sites/Laboratories

4.1. Rationale for Study Population

This is a single site study to be conducted at the Sean N Parker Center for Allergy and Asthma Research at Stanford University. We will limit our age group to 7-55 years so that we may collect adequate blood volumes for mechanistic studies. The upper age limit of 55 years was selected to reduce the risk that the patients have undiagnosed, underlying

cardiovascular conditions that could entail significant risk with the use of epinephrine in subjects exposed to the risk of anaphylaxis.

4.2. Inclusion Criteria

Individuals who meet all of the following criteria are eligible for enrollment as study participants:

1. Subject and/or parent guardian must be able to understand and provide informed consent
2. Age 7 through 55 years (inclusive)
3. Clinical history of allergy to cashew or shrimp-containing foods
4. Serum IgE to cashew or shrimp of ≥ 0.35 kUA/L [determined by UniCAP™ within the past 12 months] and/or a SPT to cashew, or shrimp ≥ 3 mm compared to control
5. Experience dose limiting symptoms at or before the 300 mg challenge dose of FA protein on Screening DBPCFC conducted in accordance with PRACTALL guidelines
6. Written informed consent from adult participants
7. Written informed consent parent/guardian for minor participants
8. Written assent from minor participants as appropriate (e.g., above the age of 7 years or the applicable age per local regulatory requirements)
9. All female subjects of child-bearing potential will be required to provide a blood or urine sample for pregnancy testing that must be negative one week before being allowed to participate in the study.
10. Use of effective birth control by female participants of child-bearing potential

4.3. Exclusion Criteria

Individuals who meet any of these criteria are not eligible for enrollment as study participants:

1. Inability or unwillingness of a participant to give written informed consent or comply with study protocol
2. History of uncontrolled cardiovascular disease, including uncontrolled or inadequately controlled hypertension
3. History of other chronic disease (other than asthma, atopic dermatitis, or allergic rhinitis) requiring therapy (e.g., heart disease, diabetes) that is, or is at significant risk of becoming unstable or requiring a change in chronic therapeutic regimen and, in the opinion of the Principal Investigator, would represent a risk to the subject's health or safety in this study or the subject's ability to comply with the study protocol.
4. History of eosinophilic esophagitis (EoE), other eosinophilic gastrointestinal disease, chronic, recurrent, or severe gastroesophageal reflux disease (GERD) grade 3 according to CTCAE version 5.0, symptoms of dysphagia (e.g., difficulty swallowing, food "getting stuck"), or recurrent gastrointestinal symptoms of undiagnosed etiology
5. Current participation in any other interventional study
6. Subject is currently in the build-up phase of immunotherapy to another allergen and is on maintenance immunotherapy dose for an allergen related to cashew or shrimp.
7. Severe asthma (NAEPP EPR-3 Medication Criteria Steps 5 or 6)
8. Mild or moderate asthma (NAEPP EPR-3 Medication Criteria Steps 1-4), if not controlled as measured by an $ACT \leq 19$,
9. A hospitalization for asthma in the past 6 months
10. ER visit for asthma within the past 6 months
11. Burst or steroid course for asthma in the past 6 months
12. Use of omalizumab or biologic therapy (e.g., infliximab, rituximab, etc.) within the past 6 months
13. Use of complementary and alternative medicine (CAM) treatment modalities (e.g., herbal remedies) for atopic and /or non-atopic disease within 90 days preceding Initial Dose Escalation Day (IDED) or at any time after the IDED

14. Use of beta-blockers (oral)
15. Pregnancy or lactation
16. Allergy to oat
17. History of severe anaphylaxis to cashew or shrimp with symptoms including hypotension requiring fluid resuscitation and/or the need for mechanical ventilation within the last year.
18. Use of investigational drugs within 12 weeks of participation
19. Past or current medical problems or findings from physical assessment or laboratory testing that are not listed above, which, in the opinion of the investigator, may pose additional risks

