
Exclusion Criteria
	
 • Inability or unwillingness of a participant to give written informed consent or comply with study protocol • History of uncontrolled cardiovascular disease, including uncontrolled hypertension • History of other chronic disease (other than asthma, atopic dermatitis, or allergic rhinitis) requiring therapy (e.g., heart disease, diabetes) that is, or is at significant risk of becoming unstable or requiring a change in chronic therapeutic regimen and, in the opinion of the Principal Investigator, would represent a risk to the subject’s health or safety in this study or the subject’s ability to comply with the study protocol. • History of eosinophilic esophagitis (EoE), other eosinophilic gastrointestinal disease, chronic, recurrent, or severe gastroesophageal reflux disease (GERD) grade 3 according to CTCAE version 5.0, symptoms of dysphagia (e.g., difficulty swallowing, food “getting stuck”), or recurrent gastrointestinal symptoms of undiagnosed etiology • Current participation in any other interventional study • Subject is currently in the build-up phase of immunotherapy to another allergen and is on maintenance immunotherapy dose for any allergen related to cashew or shrimp • Severe asthma (NAEPP EPR-3 Medication Criteria Steps 5 or 6) • Mild or moderate asthma (NAEPP EPR-3 Medication Criteria Steps 1-4), if not controlled as indicated by an $ACT \leq 19$ • A hospitalization for asthma in the past 6 months • ER visit for asthma within the past 6 months • Burst or steroid course for asthma in the past 6 months • Use of omalizumab or biologic therapy (e.g., infliximab, rituximab, etc.) within the past 6 months • Use of complementary and alternative medicine (CAM) treatment modalities (e.g., herbal remedies) for atopic and /or

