7.1.2. Other permitted concomitant medications

All subjects may continue their usual medications, including those taken for asthma, allergic rhinitis and atopic dermatitis, during the study. However, they must be able to discontinue antihistamines prior to the initial day of escalation, skin testing and all oral food challenges. Usual topical steroid use is permitted at the time of skin testing. Up-dosing will not occur within 3 days of systemic steroid use.

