7.3. Prohibited Medications

Participants will be removed from the trial if any of the following meds are started and cannot be safely stopped:

- Omalizumab (Xolair)
- Oral β -blockers

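### Exclusion 6 joins two background-immunotherapy conditions with *and*, so neither alone excludes, and the other provisions close the gap only in part

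*Combined protocol and SAP*

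**What the plan says.** Section 4.3 opens its list with the rule "Individuals who meet any of these criteria are not eligible for enrollment as study participants". Item 6 then excludes a subject who is currently "in the build-up phase of immunotherapy to another allergen and is on maintenance immunotherapy dose for an allergen related to cashew or shrimp". The matching bullet in the Protocol Synopsis reads "in the build-up phase of immunotherapy to another allergen and is on maintenance immunotherapy dose for any allergen related to cashew or shrimp". The two differ only in *an* versus *any*.

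These other provisions bear on the same candidates:

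- Exclusion 5 (Section 4.3): "Current participation in any other interventional study".
- Exclusion 18 (Section 4.3): "Use of investigational drugs within 12 weeks of participation".
- Exclusion 1 (Section 4.3) bars people who cannot or will not follow the protocol. Section 8.3 (Updosing Phase) tells participants to go on avoiding their other known food allergens.
- The last exclusion in the synopsis lets the investigator exclude for problems or findings that could affect how the data are interpreted. The body version (Section 4.3, item 19), as printed, stops at additional risks.
- Inclusion 5 (Section 4.2) requires a dose-limiting reaction no later than the 300 mg step of the screening challenge.
- Section 7.1.2: "All subjects may continue their usual medications, including those taken for asthma, allergic rhinitis and atopic dermatitis, during the study". Section 7.3 says "Participants will be removed from the trial if any of the following meds are started and cannot be safely stopped" and lists omalizumab and oral beta-blockers only.

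The primary endpoint (Section 3.2) is the week 52 change from baseline in CD28 on allergen-specific CD4+ T cells, compared between those who pass and those who fail the week 52 challenge. Section 13.4.2 adjusts for baseline CD28. Section 13.3 rules out further covariates in the primary analysis, and Section 13.4.3 adds age, sex and allergy type in sensitivity analyses. Background immunotherapy appears in none of these.

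**The concern.** Being in build-up to one allergen and being on maintenance for a related allergen are different exposures, and each is a plausible reason to keep someone out. Requiring both at once limits the exclusion to people receiving two immunotherapies simultaneously, which is an unlikely target for the rule.

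Maintenance to a related allergen matters most for the endpoint. Section 1.2 gives the plan's own rationale: T cells express less CD28 as immunotherapy proceeds. If immunotherapy to a related allergen has already acted on cashew- or shrimp-specific cells, the participant may enter with a shifted CD28 baseline, a different subsequent change, or a different chance of passing at week 52. All three feed the pass-versus-fail contrast, which rests on about 14 expected non-responders (Section 13.7).

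Build-up to an unrelated allergen raises a different issue. A second escalating exposure makes it harder to attribute a reaction to study dosing, and the stopping rules in the synopsis and the review triggers in Section 12.8.2.2 depend on that attribution.

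**Working it through.** **Step 1. Logic of item 6.** The list's *any* operates between numbered items. Within item 6 the connective is *and*.

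| Build-up to another allergen | Maintenance to a related allergen | Excluded as written | Excluded under *or* |
|---|---|---|---|
| yes | yes | yes | yes |
| yes | no | no | yes |
| no | yes | no | yes |
| no | no | no | no |

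The two middle rows are the gap. Loose drafting is not a safe explanation. Inclusion 4 and exclusions 13 and 17 write *and/or* where either condition suffices, and exclusion 3 uses *and* to join conditions that must both hold. The synopsis repeats the wording, so neither place corrects the other.

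**Step 2. What else catches the middle rows.**

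- Exclusions 5 and 18 reach immunotherapy given in another study or as an investigational product. They do not reach routine-care immunotherapy.
- The avoidance instruction in Section 8.3, with exclusion 1, sits badly with ongoing immunotherapy to another food. It is an on-treatment instruction rather than an eligibility rule, and it does not cover non-food allergens. Item 6 says allergen, not food.
- The last synopsis exclusion is discretionary and is framed around medical problems and findings. Little should be made of the shorter body version, which may be cut off in the copy read.
- The 300 mg entry requirement removes candidates already well protected against the study food. It does not remove someone partly treated who still reacts.
- Section 7.3 concerns drugs started during the study, and Section 7.1.2 does not mention immunotherapy. They show only that these sections do not close the gap.

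**Step 3. Sensitivity of the primary comparison (illustration only).** Inputs from Section 13.7: 58 responders, 14 non-responders, difference 0.75, SD of change 0.90, correlation 0.5, stated power 87%.

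I read this as a two-sided 5% ANCOVA t-test with 69 degrees of freedom:

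- Residual SD = 0.90 × √(1 − 0.5²) = 0.779.
- Standard error = 0.779 × √(1/58 + 1/14) = 0.232.
- Noncentrality = 0.75 / 0.232 = 3.23, giving power of about 89%. This is close to the stated 87% and is used below only as the reference.

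Assume a share f of the 58 responders shows no CD28 difference from non-responders, with the SD held fixed. The mean difference becomes 0.75 × (1 − f):

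| f (assumed) | Difference | Power |
|---|---|---|
| 0% | 0.750 | about 89% |
| 5% | 0.7125 | about 86% |
| 10% | 0.675 | about 82% |
| 20% | 0.600 | about 72% |

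The documents give no value for f. Complete loss of the difference in the affected participants is the severe end of what could happen.

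**The case against.** The strongest reply is that the wording is awkward but the trial is protected in practice. Each part deserves an answer.

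- **Other provisions apply.** A reader might infer from item 6 that nothing else catches these candidates. The documents do not support that: exclusions 1 and 5, the avoidance instruction and investigator discretion all reach some of them. What remains is that no named criterion clearly excludes routine-care maintenance to a related allergen.
- **The analysis adjusts for baseline CD28.** This stands in part. Adjustment deals with a shifted starting level. It does not deal with a different change from the same starting level, or with a changed chance of passing. A reader might infer a definite bias toward zero, but the direction is plausible rather than shown.
- **Entry requires a reaction by 300 mg.** This also stands in part. It weakens the argument that such people are more likely to pass, but does not remove it for those who are partly treated.
- **Unrelated build-up should not move cashew- or shrimp-specific cells.** This stands. The documents give no mechanism for it, so extending the CD28 concern to that group goes too far.
- **The lack of a concurrent untreated arm is beside the point.** This stands for the primary endpoint, which compares passers and failers who were all treated.
- **The intended rule is not stated.** This stands. Item 6 restricts maintenance only for related allergens, so some background immunotherapy was evidently acceptable.

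**Conclusion.** The drafting defect is real and appears in both operative statements of the criterion: as written, either kind of background immunotherapy alone leaves a candidate outside item 6. The consequence that holds up is narrow. A person on routine-care maintenance immunotherapy to a related allergen who still reacts by 300 mg could enrol, with possible effects on the CD28 baseline or the challenge result. For unrelated build-up, the issue is mainly attribution of reactions.

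Severity is moderate. Nothing here shows a stated power, alpha or sample size to be wrong. A reader might want a head count of affected participants, but the documents give no prevalence for either exposure, so any count would rest on invented inputs. The power figures above are what-ifs under an assumed f, not an estimate of harm. The conclusion rests on a literal reading of *and* and on the premise, plausible but not demonstrated here, that immunotherapy to a related allergen can affect T cells specific to the study food.

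**What to change.** 1. Reconcile the synopsis exclusion, Section 4.3 item 6 and the avoidance instruction in Section 8.3, and state whether each condition alone excludes. If that is the intent, as the wording suggests, replace *and* with *or* in both places or split item 6 into two numbered exclusions.
2. For participants already enrolled, use the concomitant-medication records, which Appendix 1 schedules at every visit from screening onward, to flag background immunotherapy by allergen and phase. Repeat the primary ANCOVA without the flagged participants as a prespecified sensitivity analysis.
3. Report the number flagged in each week 52 challenge group, so that readers can see whether the issue arose at all.

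The cost is a one-word change in two places plus one extra analysis on data already scheduled for collection. The downside is slightly fewer eligible candidates.
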